5.1. Randomized Set

The Randomized Set consists of all randomized participants. Participants will be analyzed according to their randomized study arm.

5.2. Full Analysis Set (FAS)

The FAS consists of all randomized participants who receive IP. Participants will be analyzed according to their randomized study arm.

5.3. Modified Intent-to-Treat (mITT) Set

The mITT Set consists of all participants in FAS who had no immunologic or virologic evidence of prior SARS-CoV-2 infection (both negative RT-PCR test for SARS-CoV-2 and negative serology test based on serum binding antibody (bAb) specific to SARS-CoV-2 nucleocapsid) pre-booster, i.e., all FAS participants with pre-booster/baseline SARS-CoV-2 negative status. Participants will be analyzed according to their randomized study arm.

5.4. Per-Protocol (PP) Set for Immunogenicity (PPSI)

The PPSI consists of all participants in the FAS who received the planned dose of study vaccination and have no major protocol deviations impact critical or key study data. Participants will be analyzed according to their randomized study arm.

5.5. Per-Protocol (PP) Set for Immunogenicity – SARS-CoV-2 negative (PPSI-Neg)

The PPSI-Neg consists of participants in the PPSI who have no serologic or virologic evidence of SARS-CoV-2 infection at baseline and up to the day of analysis visit. This is defined by both negative RT-PCR test for SARS-CoV-2 and negative serology test based on bAb specific to SARS-CoV-2 nucleocapsid (as measured by Roche Elecsys Anti-SARS-CoV-2 assay) on the day of analysis visit AND no prior positive RT-PCR test or positive test based on bAb specific to SARS-CoV-2 nucleocapsid at baseline or between baseline and the day of analysis visit.

PPSI-Neg will be the primary analysis set for analyses of immunogenicity unless otherwise specified. Participants will be analyzed according to their randomized study arm.

5.6. Modified Per-Protocol (PP) Set for Immunogenicity – SARS-CoV-2 negative (Modified PPSI-Neg)

The Modified PPSI-Neg consists of participants in the PPSI who have no serologic or virologic evidence of SARS-CoV-2 infection at baseline. This is defined by both negative

RT-PCR test for SARS-CoV-2 and negative serology test based on bAb specific to SARS-CoV-2 nucleocapsid (as measured by Roche Elecsys Anti-SARS-CoV-2 assay) at baseline.

Modified PPSI-Neg will be used for sensitivity analysis of immunogenicity. Participants will be analyzed according to their randomized study arm.

5.7. Solicited Safety Set

The Solicited Safety Set consists of all randomized participants who receive IP and contribute any solicited AR (SAR) data within the first 7 Days after IP administration.

The Solicited Safety Set will be used for the analyses of SARs within 7 Days. Participants will be included in the study arm that they actually received.

5.8. Safety Set

The Safety Set consists of all randomized participants who receive IP. The Safety Set will be used for all analyses of safety except for the SARs within 7 Days. Participants will be included in the study arm that they actually received.

5.9. Per-Protocol (PP) Set for Efficacy (PPSE)

The PPSE consists of all participants in the mITT who receive the planned dose of study vaccination and have no major protocol deviations that impact key or critical data.

6. Statistical Analysis

6.1. General Considerations

Please refer to the [Appendix E](#) for Schedule of Events (SoE).

Continuous variables will be summarized using the following descriptive summary statistics: the number of participants (n), mean, standard deviation (SD), median, minimum (min), and maximum (max).

Categorical variables will be summarized using counts and percentages.

Baseline value, unless specified otherwise, is defined as the most recent non-missing measurement (scheduled or unscheduled) collected before the administration of IP.

For the summary statistics of all numerical variables, unless otherwise specified, the display precision will follow programming standards. Refer to [Appendix A](#) for variable display standards.

When count data are presented, the percentage will be suppressed when the count is zero to draw attention to the non-zero counts. A row denoted “Missing” will be included in count tabulations where specified on the shells to account for dropouts and missing values. The denominator for all percentages will be the number of participants corresponding group, unless otherwise specified.

Baseline or pre-booster SARS-CoV-2 status is determined by using virologic and serologic evidence of SARS-CoV-2 infection on or before Day 1 (pre-booster).

Positive SARS-CoV-2 status prior to booster dose (baseline) is defined as a positive RT-PCR test for SARS-CoV-2, and/or a positive serology test based on bAb specific to SARS-CoV-2 nucleocapsid (as measured by Roche Elecsys Anti-SARS-CoV-2 assay) on or before Day 1.

Negative SARS-CoV-2 status prior to booster dose (baseline) is defined as a no indication of a positive status based on either RT-PCR test for SARS-CoV-2 or serology test based on bAb specific to SARS-CoV-2 nucleocapsid (as measured by Roche Elecsys Anti-SARS-CoV-2 assay) at Day 1.

The baseline SARS-CoV-2 status is defined as missing for participants with both tests missing, or with one test missing and one test negative.

Participants with negative baseline (pre-booster) SARS-CoV-2 status will be included in the mITT population; participants with positive or missing baseline SARS-CoV-2 status will be excluded from the mITT population.

Age: unless otherwise specified, age is calculated as the age at screening.

Study day relative to the IP injection will be calculated as below:

- a) study day prior to the IP injection will be calculated as: date of assessment/event – date of the IP injection;
- b) study day on or after the date of the IP injection will be calculated as: date of assessment/event – date of the IP injection + 1;

The following **analysis periods or stages** for safety analyses will be used for both study parts:

- Up to 28 days after vaccination: from the day of vaccination (Day 1) and continues through the earliest date of (the day of vaccination and 27 subsequent days, the day of study discontinuation). This analysis period will be used as the primary analysis period for safety analyses including unsolicited AEs, except for SARs, unless specified otherwise.
- Throughout the study: from the day of vaccination (Day 1) and continues through the earliest date of (study completion, discontinuation from the study, or death).

Unscheduled visits: Unscheduled visit measurements will be included in analysis as follows:

- In scheduled visit windows per specified visit windowing rules.
- In the derivation of baseline measurements.
- In the derivation of maximum/minimum on-treatment values and maximum/minimum change from baseline values for safety analyses.
- In individual subject data listings as appropriate.

Visit windowing rules: The analysis visit windows for protocol-defined visits are provided in [Appendix B](#).

Incomplete/missing data:

- Imputation rules for missing dates of prior/concomitant medications, non-study vaccinations and procedures are provided in [Appendix C](#).
- Imputation rules for missing or incomplete AE dates are provided in [Appendix D](#).
- If the laboratory results are reported as below the LLOQ, the numeric values will be substituted by $0.5 \times \text{LLOQ}$ in the summary when treating the results as continuous variables. If the laboratory results are reported as greater than the ULOQ (e.g., > 3000), the numeric values will be substituted by ULOQ in the summary statistics for continuous variable.
- Other incomplete/missing data will not be imputed, unless specified otherwise.

Treatment groups

Part 1

- mRNA-1273.529 50 µg, study vaccine as a 4th dose

- mRNA-1273 50 µg, study vaccine as a 4th dose.
- mRNA-1273.529 50 µg, study vaccine as a 3rd dose
- mRNA-1273 50 µg, study vaccine as a 3rd dose

Part 2

- mRNA-1273.214 50 µg, study vaccine as a 4th dose
- mRNA-1273 50 µg, study vaccine as a 4th dose.
- mRNA-1273.214 50 µg, study vaccine as a 3rd dose
- mRNA-1273 50 µg, study vaccine as a 3rd dose

All analyses and data summaries/displays for disposition, baseline demographics and characteristics will be provided by treatment group unless otherwise specified. All analyses and data summaries/display for efficacy will be provided by treatment group using the appropriate analysis population unless otherwise specified.

Subgroup Analysis

Immunogenicity will be assessed in the following subgroups:

- Age (≥ 16 to < 65 , and ≥ 65 years)
- Sex (female, male)
- SARS-CoV-2 status (negative, positive) at the day of analysis visit (e.g., for Day 29, subgroup analyses will be performed based on SARS-CoV-2 status up to Day 29 visit)
- Pre-booster SARS-CoV-2 status (negative, positive)
- Race and ethnicity group (White, Mixed or Multiple ethnic groups, Asian or Asian British, etc.)
- In addition, Phase B in each study Part (analyses may be performed in two or four subsets):
 - Two subsets
 - Subset of participants in the 4th dose group who received an additional booster outside of the study.
 - Subset of participants in the 4th dose group who did not receive an additional booster outside of the study.
 - Four subsets

- Subset of participants in the 4th dose group who were unblinded to study IP and received an additional booster outside of the study.
- Subset of participants in the 4th dose group who were unblinded to study IP and did not receive an additional booster outside of the study.
- Subset of participants in the 4th dose group who remained blinded to study IP and received an additional booster outside of the study.
- Subset of participants in the 4th dose group who remained blinded to study IP and did not receive an additional booster outside of the study.

Safety and efficacy may be assessed for the same subgroups.

Analyses Approach

All analyses and data summaries/displays will be provided by study arm (mRNA-1273.529 and mRNA-1273 for Part 1, and mRNA-1273.214 and mRNA-1273 for Part 2) and by treatment subgroups (IP administrated as 3rd or 4th dose) using the appropriate analysis population, unless otherwise specified. Data summaries for participants disposition, baseline demographics, and safety data may also be provided by treatment group.

All analyses will be conducted using SAS Version 9.4 or higher unless otherwise specified.

Immunogenicity Measures

When referring to the immunogenicity measurement, titer, concentration, or level may be used interchangeably in this document. The appropriate measure for each measure will be specified in the study TLFs.

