2.2. Secondary Objectives

2.2.1. Secondary Immunogenicity Objectives

Part 1

The key secondary immunogenicity objective is:

- To demonstrate superiority of the immune response of mRNA-1273.529 compared to mRNA-1273 booster administered as a 4th dose against the B.1.1.529 strain at Day 29 or Month 3.

Other secondary objectives are:

- To demonstrate non-inferiority of the immune response of mRNA-1273.529 compared to mRNA-1273 booster administered as a 4th dose against both the B.1.1.529 and the prototype strain at all measured time points.
- To evaluate the seroresponse rate (SRR) of mRNA-1273.529 and mRNA-1273 boosters administered as a 4th dose.

Part 2

- To evaluate the SRR of mRNA-1273.214 and mRNA-1273 boosters administered as a 4th dose.
- To evaluate the immune response of mRNA-1273.214 compared to mRNA-1273 booster administered as a 4th dose against other variant strains at Day 29 or Month 3.
- To assess for symptomatic and asymptomatic SARS-CoV-2 infection after vaccination with mRNA-1273.214 booster or mRNA-1273 booster.

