6.4. Immunogenicity Analysis

The analyses of immunogenicity will be based on the PPSI-Neg analysis population and will be performed by treatment group as defined in [Section 6.1](#).

The GMT and GM levels will be calculated using the following formula:

$$10^{\left\{ \frac{\sum_{i=1}^n \log_{10}(t_i)}{n} \right\}}$$

where t_1, t_2, \dots, t_n are n observed immunogenicity titers or levels.

The GMFR measures the changes in immunogenicity titers within participants. The GMFR will be calculated using the following formula:

$$10^{\left\{ \frac{\sum_{i=1}^n \log_{10}\left(\frac{v_{ij}}{v_{ik}}\right)}{n} \right\}} = 10^{\left\{ \frac{\sum_{i=1}^n \log_{10}(v_{ij}) - \log_{10}(v_{ik})}{n} \right\}}$$

where, for n participants, v_{ij} and v_{ik} are observed immunogenicity titers or levels for participant i at time points j and k , $j \neq k$.

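### The subgroup that is SARS-CoV-2 positive at the analysis visit pools baseline positives with post-randomisation infections, so a between-arm titre contrast in it can shift without any vaccine difference

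*SAP*

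**What the plan says.** The Subgroup Analysis list in SAP 6.1 includes "SARS-CoV-2 status (negative, positive) at the day of analysis visit". Its example for Day 29 states that "subgroup analyses will be performed based on SARS-CoV-2 status up to Day 29 visit". The next item in the same list is pre-booster status. Under Analyses Approach in the same section, "All analyses and data summaries/displays will be provided by study arm", unless otherwise specified.

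The SAP does not separately define positive at the visit. SAP 5.5 defines the negative counterpart, PPSI-Neg, as PPSI participants "who have no serologic or virologic evidence of SARS-CoV-2 infection at baseline and up to the day of analysis visit". Baseline positivity is defined in SAP 6.1: "Positive SARS-CoV-2 status prior to booster dose (baseline) is defined as a positive RT-PCR test for SARS-CoV-2, and/or a positive serology test".

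Infection after the booster is an outcome. SAP 2.2.1 gives this Part 2 secondary objective: "To assess for symptomatic and asymptomatic SARS-CoV-2 infection after vaccination with mRNA-1273.214 booster or mRNA-1273 booster". The same assessment is exploratory in Part 1 (SAP 2.3).

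On the analysis set, SAP 6.4 states: "The analyses of immunogenicity will be based on the PPSI-Neg analysis population". The subgroup list names no other set. The primary ANCOVA models (SAP 6.4.2.1.1 and 6.4.2.2.1) adjust for age group, most recent vaccine type and pre-booster titre. They have no term for infection after the booster.

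**The concern.** A subgroup fixed before randomisation keeps the randomised comparison within it. This one is fixed partly afterwards, by an event that the vaccines may influence. In people infected after dosing, the titre reflects the infection as well as the booster. If one arm has more new infections, its positive stratum holds a larger share of such people, and the two arms' strata are no longer alike.

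At stake is the reading of one supportive table in SARS-CoV-2-positive participants. A pre-booster-positive table is planned beside it. The two could disagree, and the SAP gives no rule on which to rely.

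**Working it through.** **What positive means.** Negative up to the visit requires no evidence of infection at baseline and none up to the visit (SAP 5.5). The complement, among those with known status, is baseline positive or newly infected. This is an inference, but it is the reading that fits both SAP 5.5 and the words of the Day 29 example.

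**Inputs.** The plan gives no figure to reproduce: infection rates and baseline-positive shares are not stated, and the SD and evaluable numbers are redacted. All of the following are therefore assumptions.

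- *b*: baseline-positive share, the same in both arms by randomisation.
- *a*: new-infection rate among baseline negatives, by arm.
- *R*: post-dose GMT of the newly infected divided by that of baseline positives.
- No vaccine difference within either group (true GMR = 1).

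**Formulas.** The share of newly infected among positives is w = (1−b)a / [b + (1−b)a]. The spurious unadjusted GMR, test over control, is R^(w_test − w_control).

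**Test arm 10%, control arm 20% newly infected.**

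- b = 0.2: w_test = 0.08/0.28 = 0.286, w_control = 0.16/0.36 = 0.444, difference −0.159.
- b = 0.3: w_test = 0.07/0.37 = 0.189, w_control = 0.14/0.44 = 0.318, difference −0.129.

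| R | b = 0.2 | b = 0.3 |
|---|---|---|
| 3 | 0.84 | 0.87 |
| 2 | 0.90 | 0.91 |
| 1.5 | 0.94 | 0.95 |
| 1/1.5 | 1.07 | 1.05 |
| 1/2 | 1.12 | 1.09 |
| 1/3 | 1.19 | 1.15 |

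The lower three rows are the reciprocals of the upper three.

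**A smaller contrast, 20% versus 25%.** The differences in share are 0.444 − 0.500 = −0.056 (b = 0.2) and 0.318 − 0.368 = −0.050 (b = 0.3). For R = 1.5 to 3 the factor is 0.94-0.98.

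**An early visit, 2% versus 3%, b = 0.25.** The shares are 0.015/0.265 = 0.057 and 0.0225/0.2725 = 0.083. The factor is 0.97-1.03 for R from 3 to 0.33. With b = 0.10 the range widens to 0.94-1.07.

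**Does the planned covariate adjustment remove it?** A simulation with 1,000,000 participants per arm used b = 0.25, 10% versus 20% newly infected, baseline positives' pre-booster titres 4 to 8 times higher, SD 1.2 on the natural-log scale and within-group correlation 0.5. Results are the arm with fewer infections over the arm with more (1 divided by the simulated ratio).

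| R | Unadjusted (formula) | Adjusted for pre-booster titre |
|---|---|---|
| 3 | 0.85 | 0.82-0.83 |
| 2 | 0.90 | 0.86 |
| 1 | 1.00 | 0.91-0.92 |
| 0.5 | 1.10 | 0.97-1.01 |
| 0.33 | 1.17 | 1.01-1.05 |

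Adjustment does not remove the shift. It moves the estimate further against the arm with fewer infections, because the newly infected have lower pre-booster titres than the baseline positives they are pooled with. Under these assumptions the adjusted shift changes sign only when R falls to about 0.5 or below.

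**With pre-booster status instead.** No new infections enter the positive group, so w = 0 in both arms and the factor from mixing is R^0 = 1.00.

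**The case against.** Four points can be made for the plan.

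1. *No comparison is promised.* SAP 6.1 says that immunogenicity will be assessed in these subgroups and displayed by arm. It names no GMR, SRR difference or between-arm interval for visit status. Where model-based subgroup comparisons are intended, the SAP says so, as for the Phase B subgroups in 6.4.2.1.3 and 6.4.2.2.3. This stands: a reader might infer that a GMR is pre-specified in the positive stratum, and the text does not establish it. But GMR is the between-arm measure throughout SAP 6.4.2, nothing excludes it here, and arms shown side by side invite the comparison.

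2. *The direction is not known.* A reader might conclude that the table is always biased against the more protective vaccine. The documents give no value for R. Baseline positives have had both infection and a booster, so R below 1 cannot be ruled out. This stands too.

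3. *Baseline-defined analyses are already planned.* They include the pre-booster subgroup, PPSI summaries by pre-booster status (6.4.2.1.2), PPSI models with baseline status as a factor (6.4.2.1.1, 6.4.2.2.1), and SRR stratified by pre-booster status (6.4.2.1.2, 6.4.2.2.2). This limits the harm, and it also means that the fix loses no valid information.

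4. *PPSI-Neg also conditions on infection up to the visit.* A reader might extend the point to the primary analysis or bar every between-arm contrast by visit status. That goes too far. The visit-negative stratum excludes infected participants rather than mixing two kinds of them, so this pooling does not arise there. It is essentially the primary contrast. Whether excluding infected participants selects differently by arm is a separate question.

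**Conclusion.** The point holds for the visit-status positive stratum only. That stratum pools two different groups in proportions that can differ by arm because of a study outcome, and neither a rule nor a model term separates them. If the arms differ in new infections, a between-arm contrast there can shift with no vaccine difference.

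The size is conditional. The range 0.84-0.95 needs one active booster to halve new infections relative to the other, which the documents neither state nor support, together with R of 1.5-3. A 20% versus 25% difference gives 0.94-0.98. The effect is small at Day 29 if few are infected by then, and larger at later visits if infections accumulate unequally. The sign depends on R.

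The consequence is minor. SAP 4.4 allocates alpha to the two time points and none to subgroups, and the primary objectives rest on PPSI-Neg. This is a low-cost improvement to a supportive table.

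**What to change.** In SAP 6.1, state that between-arm comparisons in SARS-CoV-2-positive participants use the pre-booster-positive subgroup already listed. If visit status is kept:

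- split positive into baseline-positive and newly infected since the booster;
- show GMTs of the newly infected by arm descriptively, without GMRs or between-arm confidence intervals;
- name the PPSI as the analysis set, because the default PPSI-Neg contains no positives.

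Leave the visit-negative contrast as it is, since it corresponds to PPSI-Neg. The cost is one edited bullet and the matching table shells. The downside is the loss of one pooled comparative table, if one was intended.

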6.2. Background Characteristics

6.2.1. Disposition

The number and percentage of participants in the following categories (analysis sets defined in [Section 5](#)) will be summarized by treatment group as defined in [Section 6.1](#):

- FAS
- mITT
- PPSI
- PPSI-Neg
- Solicited Safety Set
- Safety Set

- PPSE

The denominators of the percentages will be based on participants in the Full Analysis Set. The number of participants in the following categories will be summarized based on participants screened:

- Number of participants screened
- Number and percentage of screen failure participants and the reason for screen failure

The percentage of participants who screen failed will be based on the number of participants screened. The reason for screen failure will be based on the number of participants who screen failed.

For Solicited Safety Set, the percentage will be based on the number of participants in the treatment group within the Safety Set (as treated).

Summary of reasons for participants excluded from PP Sets will also be provided.

The number and percentage of participants in each of the following disposition categories will be summarized based on the Randomization Set:

- Received IP
- Completed study

This study treatment only consists of a one-dose booster, thus discontinuation from study treatment is not applicable in this study.

In addition, a listing of participant deaths will be provided separately.

6.2.2. Demographics and Baseline Characteristics

Descriptive statistics will be calculated for the following continuous demographic and baseline characteristics: age (years), weight (kg), height (cm), body mass index (BMI) (kg/m²). The number and percentage of participants will be provided for categorical variables such as age group, sex, race, and ethnicity.

The summaries will be provided separately based on the FAS, Safety Set, and PPSI-Neg Set.

6.2.3. Medical History

Medical history data will be coded by system organ class (SOC) and preferred term (PT) using the Medical Dictionary for Regulatory Activities (MedDRA).

The number and percentage of participants with any medical history will be summarized by SOC and PT based on the Safety Set. A participant will be counted only once for multiple events within each SOC and PT. SOC will be displayed in internationally agreed order. PT will be displayed in the sorting order described in the TLF shell document.

Medical history data will be presented in a listing.

6.2.4. Prior and Concomitant Medications

Prior and concomitant medications and non-study vaccinations will be coded using the World Health Organization (WHO) drug dictionary (WHODD). The summary of concomitant medications will be based on the Safety Set.

Categorization of prior, concomitant, and post medications is summarized in [Appendix C Table 9](#).

The number and percentage of participants using concomitant medications and non-study vaccinations during the 7-day follow-up period (i.e., on the day of injection and the 6 subsequent days) and during the 28-day follow-up period after the injection (i.e., on the day of injection and the 27 subsequent days) will be summarized by treatment group as defined in [Section 6.1](#) as follows:

- Any concomitant medications and non-study vaccination within 7 days Post Injection
- Any concomitant medications and non-study vaccination within 28 days Post Injection
- Seasonal influenza vaccine within 28 days Post Injection
- Medications to prevent pain or fever within 7 Days Post Injection
- Medications to treat pain or fever within 7 Days Post Injection

A summary table of concomitant medications and non-study vaccination that continued or newly received at or after the injection through 28 days will be provided by PT in the sorting order described in the TLF shell document.

Listings of prior, concomitant and post medications, non-study vaccination and concomitant procedures will be presented.

